3.2.5 Monthly time intervals

A month is defined as 30 days and time intervals based on monthly durations are defined as a multiple of 30 days (eg, 12 months is defined as 360 days). The following definitions of 3-month and 6-month intervals are based on 30-day months where the date of first dose of BRV is Day 1:

| Interval | Duration Definition |
|--------------|---------------------|
| Months 1-3 | Days 1-90 |
| Months 4-6 | Days 91-180 |
| Months 7-9 | Days 181-270 |
| Months 10-12 | Days 271-360 |
| Months 1-6 | Days 1-180 |
| Months 7-12 | Days 181-360 |
| Months 13-18 | Days 361-540 |
| Months 19-24 | Days 541-720 |

Subsequent 3- and 6-month intervals are defined in a similar manner.

Six-month intervals are defined for the evaluation of direct and indirect cost parameters. Statistical summaries for direct and indirect cost parameters will only present results through the first 2 years of treatment. Three-month intervals will be used for analysis of efficacy outcomes and AEs.

End date is the date of last dose of BRV.

•

For the analysis of efficacy outcomes, a subject is included in the analysis for a 3-month interval if the end date is on or after the *last day* of the 3-month interval and the subject diary was completed for at least 1 day during the 3-month interval.

For the analysis of AEs, a subject is included in the analysis for a 3-month interval if the end date is on or after the *first day* of the 3-month interval.

3.2.6 Last Value on BRV Treatment

Last Value for QOLIE-31-P, HADS, EQ-5D, and socio-professional data is the last assessment strictly after the date of first dose of BRV and up to and including the YEV at the end of the second year and any EDVs for subjects who did not complete through the YEV at the end of the second year.

Last Value for clinical laboratory parameters, vital signs, and ECGs is the last available result obtained after the first dose of BRV and prior to or on the date of last dose of BRV. All scheduled and unscheduled assessments within this time period will be considered. Last Value will be determined separately for each laboratory parameter.

3.2.7 Exposure duration and exposure duration cohorts

At the final analysis, the overall duration of exposure (or On Treatment Period) will be calculated as the date of last dose of BRV minus the date of first dose of BRV plus 1 day.

Each subject will be classified into one or more of the following exposure duration cohorts based on the duration of BRV exposure as calculated above:

| | |
|--------------|-----------|
| All subjects | ≥1 day |
| ≥3 months | ≥90 days |
| ≥6 months | ≥180 days |
| ≥12 months | ≥360 days |

This categorization will continue in 6-month increments past 12 months up to a time point that will be determined based on cumulative exposure at the time of the database lock.

3.2.8 Study visit cohorts

Study visit cohorts are defined for summaries of QOLIE-31-P, HADS, and EQ-5D. Six-month, 12-month, 18-month, and 24-month cohorts are defined. Subjects will be classified into a study visit cohort if they attend the scheduled visit at the time point defined by the cohort. For example, subjects will be included in the 18-month study visit cohort if they attend the scheduled visit at 18 months (ie, FEV at Month 18). Subjects may be classified in more than 1 cohort. Generally, subjects included in a cohort for a later visit will be included in all earlier study visit cohorts (eg, 6-month and 12-month study visit cohorts for subjects in the 18-month study visit cohort), although this may not be the case in the event of a missed visit or if an unscheduled visit is conducted in lieu of a scheduled visit.

3.3 Definition of Baseline Values

Baseline for all study outcomes will be based on baseline from the previous studies. For assessments performed at scheduled and unscheduled visits, Baseline will generally be the last result obtained or prior to the randomization visit of the previous study. Baseline will be defined separately for each hematology, blood chemistry, and urinalysis parameter.

Baseline for the evaluation of seizure frequency and seizure days will be calculated from the core study seizure diary based on the rules defined in Section 3.8.1.

3.4 Protocol deviations

The criteria for identifying important protocol deviations and the classification of important protocol deviations will be defined separately in the Specification of Protocol Deviations document. Whenever possible, criteria for identifying important protocol deviations will be implemented algorithmically to ensure consistency in the classification of important protocol deviations across all subjects.

3.5 Analysis populations

3.5.1 Safety Population

The Safety Analysis Set will consist of all subjects who took at least 1 dose of study drug.

Summaries of demographics and baseline characteristics, medical history, AEDs, non-AEDs, HADS, , study drug exposure, and safety outcomes will be provided for the Safety Analysis Set.

3.5.2 Efficacy Populations

Efficacy Analysis Sets will consist of all subjects who took at least 1 dose of study drug and have at least 1 seizure diary day during the Evaluation Period. Separate Efficacy Populations are defined for subjects with focal epilepsy from N01193, N01252, N01253, and N01254 and subjects with generalized epilepsy from N01254.

A subject will be excluded from the Efficacy Analysis Set for POS or PGS if either they did not receive at least 1 dose of BRV, or the clinical database indicates that the daily seizure diary was not completed for any days on or after the first dose of BRV and on or prior to the end date of the Evaluation Period (see Section 8).

Seizure outcomes will be summarized for either the Efficacy Analysis Set for POS or the Efficacy Analysis Set for PGS. Summaries of epilepsy history, QOLIE-31-P, and EQ-5D will be provided for the Efficacy Analysis Sets for both POS and PGS.

3.6 Treatment Assignment and Treatment Groups

This is an uncontrolled study in which all subjects receive BRV in doses that are optimally adjusted for each subject. Generally, statistical summaries will present all subjects combined as a single treatment arm unless otherwise indicated.

3.7 Coding dictionaries

Medical history and AEs will be coded using the Medical Dictionary for Regulatory Activities (MedDRA). Medications will be coded using the World Health Organization Drug Reference List (WHO-DRL). Prior and concomitant medical procedures will not be coded.

3.8 Definitions of study-specific derived variables

3.8.1 Calculation of seizure frequency/days

3.8.1.1 Initial seizure data processing

Each seizure code in the clinical database will be mapped to exactly 1 of the following codes based on the 1981 International League Against Epilepsy (ILAE) classification: I, IA, IA1, IA2, IA3, IA4, IB, IB1, IB2, IC, II, IIA, IIB, IIC, IID, IIE, IIF, or III.

With regard to cluster seizures, investigator sites are to report the number of cluster episodes rather than reporting the estimated number of individual seizures. Therefore, no imputation will be applied for the seizure counts corresponding to reports of cluster seizures.

3.8.1.2 Calculation of adjusted seizure frequency

The following derivations apply only to subjects with Partial Onset Seizures.

Baseline POS frequency for seizure types I, IA, IB, IC, and for all seizure types (I+II+III) will be obtained from the Baseline Period of the previous double-blind study.

The total number of seizures for seizure types I, IA, IB, and IC, and the total number of seizures for all seizure types (I+II+III) will be calculated overall, by 3-month time intervals, and over the cohort interval for each exposure duration cohort.

All seizure diary during evaluation period will be considered for these calculations.

Twenty-eight day adjusted seizure frequency for seizure types I, IA, IB, and IC, and for all seizure types (I+II+III) will be calculated overall, within each 3-month time interval, and over each exposure duration cohort interval by dividing the total number of seizures for each seizure type by the number of days for which the diary was completed overall, within each 3-month interval, and within each exposure duration cohort interval, and multiplying the resulting value by 28.

3.8.1.3 Calculation of adjusted seizure days

The following derivations apply only to subjects with All Other Seizure Types, based on the 1981 ILAE classification, All Other Seizure Types include the generalized seizure types and unclassified seizure types.

Baseline seizure days for seizure types II, IIA through IIF, and for all seizure types (I+II+III) will be obtained from the Baseline Period of the previous study.

The total number of seizure days for seizure types II, IIA through IIF, and the total number of seizure days for all seizure types (I+II+III) will be calculated overall, by 3 month time intervals, and over the cohort interval for each exposure duration cohort. The same seizure diary data defined in the Section 3.8.1.2 for POS frequency will be considered.

Twenty-eight day adjusted seizure days for seizure types II, IIA through IIF, and for all seizure types (I+II+III) will be calculated overall, within each 3-month time interval, and over each exposure duration cohort interval by dividing the total number of seizure days for each seizure type by the number of days for which the diary was completed overall (ie, over the periods defined in the Section 3.8.1.2), within each 3-month interval, and within each exposure duration cohort interval, and multiplying the resulting value by 28.

3.8.2 QOLIE-31-P

The QOLIE-31-P is an adaptation of the original QOLIE-31 (Cramer et al, 1998). The QOLIE-31-P includes 30 items grouped into 7 multi-item subscales (seizure worry [5 items], overall quality of life [2 items], emotional well-being [5 items], energy/fatigue [4 items], cognitive functioning [6 items], medication effects [3 items], and social function [5 items]) and a health status item. The QOLIE-31-P total score, subscale scores, and health status item score are calculated according to the scoring algorithm described below, with scores ranging from 0 to 100 and higher scores indicating better functioning. In addition to these 31 items,

the QOLIE-31-P includes 7 items assessing the degree of “distress” associated with the topic of each subscale (ie, distress items) and 1 item asking about the relative importance of each subscale topic (ie, prioritization item).

Subscale Scores

As a first step to calculating the subscale scores, the individual responses for the 30 subscale items are rescaled to a 0 to 100 scale with higher scores reflecting better functioning; the rescaled values for each item are defined in Section 13.1. Each subscale score is then calculated by summing the rescaled responses for that subscale and dividing by the number of items without a missing response. A subscale score will be calculated only if at least 50% of the items within the subscale are present.

Total Score

Total score is calculated as a weighted sum of the subscale scores based on the weighting in Section 13.1. Total score will be missing if at least 1 subscale score is missing. Total score will range from 0 to 100 with a higher score reflecting better functioning.

Health Status Item

Responses for the health status item is a multiple of 10 ranging from 0 to 100 with a higher score corresponding to a better health status. The health status item response is analyzed without rescaling.

Distress Items

Each subscale includes 1 distress item. The response for each distress item is an integer ranging from 1 to 5. The response for each distress item will be converted to a 0 to 100 scale (ie, 0, 25, 50, 75, and 100) with a higher score corresponding to greater distress.

Prioritization Item

The response for each subscale for the prioritization item is an integer ranging from 1 to 7. The prioritization ranking is analyzed without rescaling.

3.8.3 HADS

The HADS assessment consists of 14 items that are each scored on a 4-point scale ranging from 0 to 3, with a higher score corresponding to worse anxiety or depression. The depression and anxiety scores will be calculated by summing the scores for the items corresponding to each subscale, as described in the Hospital Anxiety and Depression Scale Manual (Snaith and Zigmond, 1994): the depression score is calculated as the sum of all even-numbered items; the anxiety score is calculated as the sum of all odd-numbered items. Scores for each subscale range from 0 to 21, with higher scores corresponding to a greater level of anxiety or depression.

Missing items will be replaced by the mean of non missing items from the same subscale when calculating the above, provided at least 50% of the items (ie, at least 4 of 7 items) within the subscale are present. A subscale score will not be calculated if more than 50% of the items are missing within a subscale. This rule applies separately to the subscale scores for

anxiety and depression; for example, it may be possible to calculate the depression score in cases where the anxiety score is not calculated due to non response.

3.9 Subject site transfers

Subjects may have transferred from one site to another through the course of participation in the study. Subjects that transferred from one site to another site, for whatever reason, have generally retained their subject number. However, in some cases, the subject number changed. When this is true, the most recently assigned subject number will be used for analyses and subject data listings. A record of any change in subject numbers will be presented in the Section 13.2.

4 STATISTICAL/ANALYTICAL ISSUES

4.1 Adjustments for covariates

No statistical testing is planned; therefore, this section is not applicable.

4.2 Handling of dropouts or missing data

Seizure frequency (subjects with POS) and seizure days (subjects with PGS) will be calculated over non missing diary days during each study period or time interval as described in Section 3.2.4 and Section 3.2.5 ; diary days for which seizure data were not obtained will not be considered in the calculation of seizure frequency or seizure days. Because the evaluation of efficacy is not the primary objective of this study, and because this is an uncontrolled study in a variable setting, which allows individualized optimization of dosing of BRV and concomitant AEDs, no summaries assessing the impact of missing seizure diary days are planned.

For subjects who prematurely discontinue during the Evaluation Period, the calculation of POS frequency and PGS seizure days will be based on available seizure diary while the subject was receiving BRV. The presence of such dropouts may influence the evaluation of the long-term outcomes for subjects who either do not discontinue or do not discontinue early in the study. Therefore, as described below, selected summaries will be produced by exposure duration cohorts to allow an assessment of long-term outcomes without the potentially confounding influence of earlier discontinuations.

4.3 Interim analyses and data monitoring

Interim summaries may be produced to support regulatory submissions for marketing authorization while this study is ongoing. There are no statistical concerns with such interim assessments for this study design.

4.4 Multicenter studies

Efficacy and safety outcomes will not be assessed for individual investigator sites due to the low expected number for enrollment within each investigator site.

4.5 Multiple comparisons/multiplicity

No statistical testing is planned; therefore, this section is not applicable.

4.6 Use of an “Efficacy Subset” of subjects

All subjects who receive at least 1 dose of study drug and have at least 1 diary record during the Evaluation Period will be included in efficacy summaries. No additional efficacy subsets are defined for this study.

4.7 Active-control studies intended to show equivalence

This section is not applicable for this study.

4.8 Examination of subgroups

Selected summaries will be provided for the following subgroups as specified within each of the following sections;

- Seizure type (Partial Onset Seizures, Primary Generalized Seizures)
- Geographic region (Latin America, North America, Asia/Pacific/Other). A mapping of countries to geographic regions is defined as

| Geographic Region | Country |
|--------------------|---|
| North America | Canada, United States, Puerto Rico |
| Latin America | Brazil, Mexico |
| Asia/Pacific/Other | Australia, Hong Kong, India, Israel, Japan, Singapore, South Africa, Republic of Korea, Taiwan, Tunisia |

- Randomized treatment in the previous study (placebo [PBO], BRV) (TEAEs only)

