2.1.2 Secondary objectives

To evaluate the maintenance of efficacy over time of BRV (for subjects with partial onset seizures [POS] and subjects with primary generalized seizures [PGS])

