3.2 Analysis time points

3.2.1 First and last dose of BRV

Unless otherwise noted, all references to the first dose of BRV in this SAP refer to the first dose of BRV during N01199 (ie, not the first dose of BRV from the previous study in which subjects participated in prior to N01199). Unless otherwise noted, all references to the last known dose of BRV in this SAP refer to the last dose of BRV taken across any study periods (ie, not necessarily the last dose of BRV during the Evaluation Period).

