8.1.2 Percent reduction in POS frequency

Percent reduction in POS frequency from Baseline to the On Treatment Period will be calculated as follows, where On Treatment Period Frequency is the 28-day adjusted POS frequency during On Treatment Period and Baseline Period Frequency is the 28-day adjusted POS frequency during the Baseline Period of the previous study.

$$\% \text{ Reduction} = 100 \times \frac{\text{Baseline Period Frequency} - \text{On Treatment Period Frequency}}{\text{Baseline Period Frequency}}$$

A similar calculation applies to each 3-month time interval over the On Treatment Period and for the cohort interval for each exposure duration cohort.

Percent reduction from Baseline for POS frequency will be summarized with quantitative descriptive statistics for the On Treatment Period, and by 3-month time intervals over the On Treatment Period. The summary over the On Treatment Period will include all subjects in the POS Efficacy Analysis Set. Similar summaries will be provided for the full cohort interval and by 3-month time intervals for each exposure duration cohort. Percent reduction from Baseline for POS frequency will be summarized in the same manner by geographic region.

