8.1.3 Responder rate for POS frequency

Responders over the On Treatment Period are defined as subjects with a 50% or greater reduction in 28-day adjusted POS frequency from Baseline to the On Treatment Period. A similar calculation applies to each 3-month time interval over the On Treatment Period and for the cohort interval for each exposure duration cohort.

The number and percentage of responders for POS frequency will be summarized for the On Treatment Period, and by 3-month time intervals over the On Treatment Period. The summary over the On Treatment Period will include all subjects in the POS Efficacy Analysis Set. Similar summaries will be provided over the full cohort interval and by 3-month time intervals for each exposure duration cohort. Responder rates for POS frequency will be summarized in the same manner by geographic region.

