11.2.2 General summaries of TEAEs

Pre-treatment AEs will be provided in a subject data listing; no summaries of pre-treatment AEs are planned.

An overall summary of AEs will provide the overall number of TEAEs and the numbers and percentages of subjects with at least 1 TEAE, with a TEAE that led to permanent discontinuation of study drug, with a drug-related TEAE, with a severe TEAE, with a treatment-emergent SAE, and with a drug-related treatment-emergent SAE. The number and percentage of subjects who died will also be summarized. This summary will be provided for all subjects in the Safety Analysis Set and also by subgroup for geographic region and seizure type.

The following summaries of TEAEs will be provided by MedDRA SOC and PT. All summaries are for the combined Evaluation, Down-Titration, and Post-Treatment Periods unless otherwise indicated.

Overall Incidence Summaries

- Incidence of TEAEs
- Incidence of TEAEs by 3-month time interval
- Incidence of TEAEs by study period (Evaluation, Down-Titration, Post-Treatment)
- Incidence of TEAEs for TEAEs occurring in at least 5% of subjects
- Incidence of TEAEs by 3-month time intervals for TEAEs occurring in at least 5% of subjects overall
- Incidence of non-serious TEAEs occurring in at least 5% of subjects

The incidence of TEAEs occurring in at least 5% of subjects will be summarized overall as noted above and also by subgroup for geographic region, seizure type, and randomized treatment from the previous double-blind study.

A subject is included in a 3-month interval if the subject was receiving BRV at any time during that interval based on their duration of exposure to BRV (eg, a subject with exposure for 91 days is included in the time interval for Months 1-3 and Months 4-6). Summaries of AEs by 3-month intervals will include all subjects who are classified into each time interval

as defined above. TEAEs which had onset prior to or on the date of the last dose of BRV are included in summaries by 3-month time intervals.

Maximum Intensity and Causality

- Incidence of TEAEs by maximum intensity
- Incidence of drug-related TEAEs

Serious Adverse Events

- Incidence of treatment-emergent SAEs

Discontinuations due to TEAE

- Incidence of TEAEs leading to permanent discontinuation of study drug

TEAEs of interest

AEs of interest will be identified based on MedDRA search criteria, which are documented outside of the SAP. The following summaries will be provided for AEs of interest:

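### Early 3-month efficacy summaries mix first BRV exposure with continued exposure, and the SAP does not plan the prior-arm split that would separate them

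*SAP*

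**What the plan says.** The secondary objective is "To evaluate the maintenance of efficacy over time of BRV" (SAP 2.1.2).

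**Time axis.** SAP 3.2.1 says that references to the first dose "refer to the first dose of BRV during N01199", whatever BRV a subject took in the feeder study. SAP 3.2.5 builds 90-day intervals from that day, and SAP 3.2.7 measures exposure duration, and so the exposure cohorts, from the same day.

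**Efficacy subgroups.** POS frequency (8.1.1), percent reduction (8.1.2) and responder rate (8.1.3) are summarised overall, by 3-month interval and within exposure duration cohorts. The only subgroup named is region: "Percent reduction from Baseline for POS frequency will be summarized in the same manner by geographic region" and "Responder rates for POS frequency will be summarized in the same manner by geographic region". Section 8.1.1 names none. The seizure-day outcomes in 8.2.2.1 to 8.2.2.3 follow the POS pattern. Prior arm appears in SAP 4.8 only as "Randomized treatment in the previous study (placebo [PBO], BRV) (TEAEs only".

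**TEAE subgroups.** For the table of TEAEs at the 5% threshold, SAP 11.2.2 reads: "summarized overall as noted above and also by subgroup for geographic region, seizure type, and randomized treatment from the previous double-blind study". The interval version is a separate bullet: "Incidence of TEAEs by 3-month time intervals for TEAEs occurring in at least 5% of subjects overall". No subgroup is attached to that bullet.

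**The concern.** SAP 2.3 describes all four feeder studies as placebo-controlled, so entrants include former-placebo and former-BRV subjects. For former-placebo subjects, Months 1-3 of N01199 show the onset of effect and of adverse reactions. For former-BRV subjects without a gap, the same interval shows continued treatment. Only the second group can show whether an effect already obtained is being kept.

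When the two are averaged, a rise in one group can offset a fall in the other, and a flat pooled line may be read as maintenance when it is not.

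On safety, SAP 11.2.1 classes AEs with onset before the first N01199 dose as pre-study, and 11.2.2 only lists them. Early reactions that former-BRV subjects had in the feeder study therefore fall outside the TEAE tables. A pooled Months 1-3 incidence then understates what first-time users experience, if former-BRV subjects have fewer events in that window.

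**Working it through.** The plan gives no figure to reproduce: there is no sample size calculation and all summaries are descriptive (SAP 2.4, 3.1). The check has three steps.

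**1. Size of the time offset.** SAP 3.2.3 gives the feeder visit used at entry: Week 7 (N01193), Week 12 (N01252/N01253) and Week 16 (N01254). The assumptions are that these weeks count from the start of treatment and that there was no gap. Prior days = 7 × weeks; offset in intervals = prior days / 90.

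| Feeder study | Prior days | Intervals | BRV days in N01199 Months 1-3 | BRV days in Months 4-6 |
|---|---|---|---|---|
| N01193 | 49 | 0.54 | 50-139 | 140-229 |
| N01252/N01253 | 84 | 0.93 | 85-174 | 175-264 |
| N01254 | 112 | 1.24 | 113-202 | 203-292 |
| Former placebo (any) | 0 | 0 | 1-90 | 91-180 |

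A former-BRV subject is thus about half to one and a quarter intervals ahead of a former-placebo subject in the same column.

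**2. What pooling can hide.** Let p be the former-placebo share. The documents do not give it, so 20-50% is assumed. Pooled change = p × (change in former placebo) + (1 − p) × (change in former BRV). If the pooled rate is flat, the hidden former-BRV loss is gain × p / (1 − p).

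- Assumed 10-point gain: 10 × 0.2/0.8 = 2.5 points; 10 × 0.5/0.5 = 10 points.
- Assumed 5-point gain: 5 × 0.2/0.8 = 1.25 points; 5 × 0.5/0.5 = 5 points.

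For TEAEs, assume a Months 1-3 incidence of 50% in former-placebo and 35% in former-BRV subjects, and 35% in both afterwards. The pooled Months 1-3 figure is 0.2 × 50 + 0.8 × 35 = 38.0%, up to 0.5 × 50 + 0.5 × 35 = 42.5%. The pooled table then falls by 3.0 to 7.5 points to reach 35%, all of it from the former-placebo subjects.

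These rates are illustrations; none comes from the documents.

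**3. Would a split be readable?** Total enrolled is 668 (SAP 2.4), POS and PGS together. The worst-case 95% half-width for a percentage is 1.96 × √(0.25/n).

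- p = 20%: n = 134 and 534, half-widths 8.5 and 4.2 points.
- p = 50%: n = 334 and 334, half-widths 5.4 points each.

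This is usable for early intervals. The POS set alone is somewhat smaller. The PGS group is described only as a minority from N01254, so its cells would be sparse.

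**The case against.** The strongest reply is that the exposure duration cohorts already protect the time trend. Both prior arms use the same pretreatment baseline (Protocol 13.1.3, SAP 3.3), and within a cohort the arm mix is essentially fixed. A reader might infer that the maintenance trend is confounded by prior arm. The documents do not support that for the cohort summaries, because a changing mix cannot drive them. The mix could shift only in the all-subjects interval summaries, and only if dropout differs by prior arm. What survives is narrower: the cohorts count from the same N01199 dose, so each one still averages two time origins.

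Further points on that side, which largely stand:

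- The offset is short beside a study that reports retention to 60 months. It affects mainly Months 1-3 against Months 4-6.
- The size depends on the chosen rates. Suppose former-BRV responders fall from 48% to 42%, former-placebo responders end at 45%, and the former-placebo share is 25%. If former-placebo subjects start at 30%, the pooled rate goes from 0.25 × 30 + 0.75 × 48 = 43.5% to 0.25 × 45 + 0.75 × 42 = 42.75%, and the loss almost vanishes. If they start at 42%, it goes from 46.5% to 42.75%, and much of the loss shows.
- Former-BRV rows are not a clean cohort. Some subjects had a treatment gap (category 3, SAP 3.2.3). The feeder arms (Protocol 6.3) and the entry doses in SAP 2.3 imply that some changed dose at entry, and later dose and AED changes were allowed.
- Protocol 13.3.4 leaves subgroups to the SAP, efficacy is secondary, and no test is affected. There is no breach of the protocol.

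A reader might also infer that TEAEs by prior arm are missing. They are not: the overall table at the 5% threshold is split. For the interval version the natural reading is that it is not split, but the sentence refers back to bullets that include it, so the text is unclear rather than plainly deficient.

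**Conclusion.** The point holds in limited form. Early 3-month efficacy summaries combine first exposure with exposure already 49, 84 or 112 days old, and the plan offers no display that separates them. This can blur early maintenance and has little bearing on multi-year intervals. Its true size cannot be computed; the 2.5 to 10 points above is a conditional illustration resting on an assumed 20-50% former-placebo share and an assumed 10-point gain. The offset itself rests on feeder weeks counting from treatment start and on no gap before N01199.

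For TEAEs, what is missing is a clear statement about the 3-month table. The remedy is a worthwhile, low-cost improvement to descriptive output and does not correct an invalid analysis.

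**What to change.** - **SAP 4.8:** extend prior randomised arm (PBO, BRV) from TEAEs to efficacy.
- **SAP 8.1.2 and 8.1.3:** add POS percent reduction and responder rate by prior arm and 3-month interval, at least through Month 12 and within the exposure duration cohorts. Footnote subjects with a treatment gap before N01199 (category 3, SAP 3.2.3) or show them separately.
- **SAP 11.2.2:** state that the 3-month table of TEAEs in at least 5% of subjects is also given by prior arm.
- **Interpretation:** read early maintenance from the gap-free former-BRV rows, noting that dose and concomitant AED changes still limit what they show.
- **PGS:** leave the split optional, because cells would be small.

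The cost is more output and wider uncertainty in the smaller group. No new data are needed, since the SAP already plans to use the prior-arm variable for TEAEs.
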